## 1. Introduction

[figure not shown]
In 2019, 7.97 million South Africans (22.7% of adults) were living with HIV. Uptake of HIV testing has been undermined by a combination of factors, including HIV stigma, distrust in the health system, skepticism toward allopathic medicine, a preference for traditional medicine, and distance to the nearest health facility. The unique sociocultural identities and generalized HIV epidemic in South Africa may require a focus on different socially stigmatized categories. Community members with low socioeconomic status (SES), as well as those who are male, younger, immigrants, harbor distrust toward allopathic medicine, and those with higher anticipated HIV stigma are more likely to seek care from a traditional healer and have lower odds of, or delayed, HIV testing. Innovative campaigns aimed at testing individuals who are less likely to visit health facilities include: home-based testing, testing in bars, testing at sports events, and distribution of self-testing kits. All are available in many parts of rural South Africa. These interventions, while yielding successes, still miss 12-20% of the population. South Africa has made progress towards their 90-90-90 targets, yet a substantial proportion of the population do not test regularly, only 33.9% of adults in rural Agincourt, Mpumalanga province (our study population, and the province with the second highest HIV prevalence in the country) received an HIV test in the past year. Interventions that engage those with one or more of the above overlapping demographics/characteristics are needed to maximize HIV prevention.

Annual community-based HIV testing, mobile testing, self-testing and clinic-based testing opportunities are available to people living in Agincourt, South Africa. Despite these ongoing efforts, testing uptake remains low. People with low SES, high levels of HIV stigma, immigrants, men, and those who distrust the allopathic health system are less likely to receive regular HIV testing and more likely to visit a traditional healer. In 2019, 7.97 million South Africans (22.7% of adults) were living with HIV with women bearing a disproportionate burden (26.6% among females vs. 14.8% among males). Though women bear a larger HIV burden, rural South Africa's "hidden HIV population" comprises patients that the allopathic health system fails to reach. In Mpumalanga province, only 33.9% of adults aged 15-59 received an HIV test in the past year. Undiagnosed HIV infection is highest among men, those with low SES, those with high perceived HIV stigma, and those who believe a traditional healer can cure HIV or deny the existence of the disease. Fear of stigma and discrimination, harmful gender norms, confidentiality fears, and a lack of policies supporting these populations render them reluctant to utilize clinic-based testing. We propose to create a new testing option to test those individuals for whom other testing mechanisms fail.

While extremely successful, community-based HIV testing is still refused by 12-20% of the population. In a rigorous systematic review of 117 community-based testing strategies in 16 African countries, index, self, mobile, and door-to-door testing achieved the highest uptake (88%, 87%, 87% and 80%, respectively). While we have eliminated the need for people to travel for their test (e.g. mobile testing), ensured confidentiality (self-testing), and targeted those at high-risk (index testing), South Africa still has a testing and linkage to care gap among difficult to reach subpopulations. People who perceive, experience or internalize stigma or other forms of marginalization are more likely to utilize traditional healers, less likely to seek care at a health facility, and less likely to undergo HIV testing.

Stigma continues to impact HIV testing uptake but needs to be addressed in a broader context. A review by Musheke of qualitative factors impacting uptake of HIV testing in sub-Saharan Africa (SSA) found structural (health care organizations, delivery, and costs), social (HIV stigma), and individual belief (trust, health belief) factors all served as barriers to HIV testing (Figure 1). It further concluded that HIV stigma is "inextricably linked" with gender, reproductive norms and economic support, suggesting that in SSA, where much of the HIV epidemic remains generalized, a broad assessment of HIV stigma in the context of gender norms and SES is needed. Individuals

**Figure 1: Factors affecting uptake of HIV testing (after Musheke et. al 2013)**

who are already marginalized from society or the health care system (low SES, immigrants, men) may be even more vulnerable to the negative impact of HIV stigma. Yet few studies have addressed this broader context of stigma.

In Nigeria, Babalola et al. found that among women, individual-level HIV stigma was negatively associated with willingness to test for HIV, while among men, community-level HIV stigma was negatively associated with a willingness to test. More recently in South Africa, and in contrast to Babalola et al., Treves-Kagan et al. found that community-level HIV stigma was negatively associated with HIV testing among women, while individual-level stigma was associated with low HIV testing among men. These studies highlight the complex nature of stigma and the large gap that exists in our understanding of its impact on testing. Given low levels of testing among some subgroups, interventions should simultaneously address this confluence of factors (stigma, gender, SES, health care system barriers, mistrust) to maximize HIV prevention interventions.

Traditional healers see patients who avoid allopathic health services, including those who refuse HIV testing. Patients report a general preference for traditional healers, given their fluency in local language, the length of time they spend with patients, the respect they show patients, the cultural congruity to their diagnosis, and their proximity to the patients. Reports of poor treatment by health care providers are common in SSA, often resulting in patients refusing or delaying allopathic health services and/or seeking alternative health services. Men, immigrants, and those with low SES most frequently report poor treatment at the health facility or report that the health system is not designed for their needs. People who first visit a traditional healer for HIV-associated symptoms before seeking an HIV test are delayed 2.4 times longer in seeking health services than those who do not. Among patients enrolled in HIV care and treatment, a preference for traditional medicine impacts their treatment decisions: patients who report use of both traditional and allopathic services are 45% less likely to enroll in antiretroviral therapy (ART) services.

Healers are respected members of their communities, play an integral role as informal referral agents to the South African health system, and act as supportive providers to patients living with chronic disease, if effectively engaged. In rural South Africa, traditional healers provide

physical and psychological services to >80% of the population. There are more than 200,000 traditional healers in South Africa, but only 46,000 registered physicians (> 20:1 ratio) who provide services for a myriad of disease conditions, including HIV, TB, malaria, epilepsy, schizophrenia, and depression. Given the level of trust in the community and the numbers of healers, partnerships may facilitate diagnosis and linkage to care via the creation of unique testing locations. It is up to researchers and health care providers to overcome our own biases and/or prejudices against this workforce to develop an effective strategy to increase testing uptake.

Traditional healers can bridge the testing gap between “non-testers” and the allopathic health system. Traditional healers have been successfully engaged in health systems to promote care linkage among people living with diabetes, TB, HIV, malaria, and mental illness- many of whom initially did not believe in their allopathic diagnosis until a healer convinced them that their condition was not caused by a curse. Those who are hesitant to test need a trusted and culturally concordant provider (traditional healer) to both vouch for and deliver the HIV test, and the same provider to create a bridge to the allopathic health facility, providing a metaphorical “safe space” for the patient while they transition to HIV care. Traditional healers are strongly motivated to play this role for two reasons: (1) Better patient health outcomes are strongly correlated with perceived quality of traditional healer care. Healers do not want to be associated with high levels of morbidity or mortality, as it is bad for business; and (2) Healers are excited at expanding their public health services. As allopathic medical knowledge is disseminated, healer views on disease causation are expanding to include the germ theory of disease. Patients are open to this partnership, given their inclination to ping-pong between the two systems depending on their needs.

## **2. Objectives**

The objective of this proposal is to conduct a pilot test of a program aimed at training traditional healers to conduct HIV testing and implementing HIV testing among people living in Bushbuckridge, South Africa.

Pilot Healer-initiated HIV testing uptake and linkage to prevention services. Trust in allopathic health care and HIV stigma will be measured among participants at study enrollment and at month seven.

*Hypothesis:* HICT will increase trust in allopathic health care and reduce HIV stigma.

## **4. Study Population**

### Population

Traditional healers, people seeking care from traditional healers, and biomedical practitioners (including clinicians and nurses) providing patient care in the Bushbuckridge area.

### Inclusion Criteria

1. Traditional healers  $\geq$  18 years of age, who are registered as traditional healers with the government of South Africa, are currently practicing in the Bushbuckridge area, and are trained to provide HIV testing.
2. Biomedical practitioners  $\geq$  18 years of age, who are currently providing HIV-related health care services to patients at government or private health facilities in Bushbuckridge.
3. Community members  $\geq$  18 years of age, who have not received an HIV test result in the past year and who currently live in Bushbuckridge.

### Exclusion Criteria

1. Traditional healers who do not pass their HIV counseling and testing certification.
2. Biomedical practitioners who do not interact with patients seeking treatment for HIV.
3. Community members who are not out sound mind or body during the recruitment (inebriated, too sick to leave the house) and community members with a previous positive HIV test result.

### Calculation of Sample Size & Sampling Strategy

We anticipate approximately 5%, perhaps 10%, of study participants will test positive for HIV and not be eligible for the analysis of health facility HIV testing within 6 months among those testing **HIV negative or refusing testing**. We further estimate that 70% will complete the healer-initiated HIV test, 60% will participate in additional counseling sessions, and 50% will attend an open house. Because study participants had no history of HIV testing in the prior year, we anticipate the primary endpoint of uptake of HIV testing at the health facility will be low, approximately 30%. Finally, given the importance of identifying sub-groups which may benefit the most from the intervention components, we have powered our study to detect significant associations within strata of potential modifiers (e.g., gender). We utilized Stata psim command to conduct 500 simulations each for all combinations of the parameters described above to estimate power to detect a range of RRs.

Given our sample size of 600 study participants, with 5% testing HIV+, and for a modifying variable distributed 50%/50%, we have ~90% power to detect stratum-specific RRs of 2.0 for each intervention component (Table 1). We still retain >80% power to detect RRs of 2.25 even if uptake of HIV testing in control group is as low as 20%. Similarly, if the modifying variable is distributed 40%/60%, we retain ≥80% power to detect stratum-specific RRs of 2.0 (Table 2). Thus, the high power due to our sample size allows for robust assessment and identification of intervention associations within key subsets of participants (gender, stigma, etc.).

Given that we only anticipate 10-30 participants to test HIV+, we will be underpowered to detect a meaningful association for how the intervention components associate with uptake of ART services at the health facility within three months among those testing **HIV positive**. However, the proportion testing positive, the proportion linking to ART care, and the magnitude of the RR for the intervention components will provide important preliminary data for whether this intervention improves ART care and retention, and not just linkage to HIV prevention services (such as follow-up HIV testing in those who are negative).

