**Table 1.**

Stratum specific sample size*	Baseline uptake of health facility HIV testing	Intervention component distribution	Power for relative increase in HIV testing uptake among those with the intervention component vs. those without		
			RR=1.75	RR=2.0	RR=2.25
135	20%	40%	0.484	0.702	0.856
		50%	0.458	0.724	0.868
		60%	0.432	0.622	0.824
		70%	0.346	0.576	0.762
135	25%	40%	0.628	0.852	0.954
		50%	0.596	0.832	0.952
		60%	0.604	0.814	0.964
		70%	0.501	0.708	0.874

135	30%	40%	0.772	0.924	0.994
		50%	0.738	0.928	0.996
		60%	0.726	0.924	0.998
		70%	0.592	0.850	0.976
135	35%	40%	0.868	0.990	1.000
		50%	0.832	0.974	1.000
		60%	0.830	0.980	1.000
		70%	0.744	0.952	0.996
135	40%	40%	0.922	1.000	1.000
		50%	0.924	1.000	1.000
		60%	0.932	1.000	1.000
		70%	0.852	0.990	1.000

\*N=135 assumes ~10% test HIV+ and are excluded and the remaining participants are divided equally into two strata of a modifier (e.g., 50% female)

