**Table 2.**

Stratum specific sample size*	Baseline uptake of health facility HIV testing	Intervention component distribution	Power for relative increase in HIV testing uptake among those with the intervention component vs. those without		
			RR=1.75	RR=2.0	RR=2.25
115	20%	40%	0.464	0.660	0.814
		50%	0.412	0.596	0.802
		60%	0.346	0.536	0.770
		70%	0.298	0.468	0.654
115	25%	40%	0.574	0.780	0.928
		50%	0.546	0.782	0.932
		60%	0.536	0.746	0.898
		70%	0.412	0.624	0.820
115	30%	40%	0.646	0.896	0.974
		50%	0.676	0.902	0.986
		60%	0.638	0.852	0.958
		70%	0.516	0.796	0.934
115	35%	40%	0.796	0.972	0.998
		50%	0.802	0.972	0.998
		60%	0.716	0.958	0.998
		70%	0.638	0.910	0.994
115	40%	40%	0.908	0.992	1.000
		50%	0.914	0.996	1.000
		60%	0.858	0.990	1.000
		70%	0.794	0.986	1.000

\*N=115 assumes ~5% test HIV+ and are excluded and the remaining participants are divided unequally into two strata of a modifier (e.g., 40% female or other modifier)

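### The stated sample size is 600, but both power tables and the expected HIV-positive count belong to a study of about 300

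*Combined protocol and SAP*

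**What the plan says.** Under Calculation of Sample Size & Sampling Strategy, the protocol introduces its power claim with "Given our sample size of 600 study participants, with 5% testing HIV+, and for a modifying variable distributed 50%/50" and makes three statements:

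- about 90% power for a stratum-specific RR of 2.0 for each intervention component, citing Table 1;
- more than 80% power for an RR of 2.25 if control-group uptake is as low as 20%;
- at least 80% power for an RR of 2.0 with a 40/60 modifier, citing Table 2.

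The footnotes give the derivation of the stratum sizes. Table 1: "N=135 assumes ~10% test HIV+ and are excluded and the remaining participants are divided equally into two strata". Table 2: "N=115 assumes ~5% test HIV+ and are excluded and the remaining participants are divided unequally into two strata".

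The same section puts HIV positivity at 5%, perhaps 10%, and says of the ART-linkage analysis: "Given that we only anticipate 10-30 participants to test HIV+, we will be underpowered". It expects 70%, 60% and 50% of participants to receive the three components, and about 30% baseline uptake of facility testing.

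**The concern.** Each footnote states fully how its stratum size was reached, so it can be solved backwards for the total. Two footnotes with different assumptions both return about 300, which looks like a change of total that was not carried through. The text also cites Table 1 at 5% HIV-positive, while that table's footnote uses 10%.

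As written, the sample-size justification does not justify the stated sample size. If 600 is the target, the quoted powers and detectable effects are not those of this study, and the ART-linkage group is planned at about half its expected size. If about 300 is the target, the text credits 600 participants with power calculated for half that number. A reader cannot tell how many people the study needs, in a population the protocol itself calls vulnerable. The pilot is also meant to help power a later randomised trial, so the ambiguity could carry forward.

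**Working it through.** **Inputs.** Total 600; HIV-positive 5% to 10%; component shares 70%, 60% and 50%; baseline uptake 30% (20% as the low case); RR 2.0 and 2.25, all from the sample-size section. Stratum sizes 135 and 115 come from the table footnotes. The model is modified Poisson regression (Data Analysis). Alpha is not stated; two-sided 0.05 is assumed here.

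**Step 1: total implied by each footnote.** Stratum n = N × (1 − HIV-positive share) × stratum share, so N = n / [(1 − HIV-positive share) × stratum share].

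- Table 1: 135 / (0.90 × 0.50) = 300.
- Table 2: 115 / (0.95 × 0.40) = 302.6.

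**Step 2: strata under each total.**

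| | N = 300 | N = 600 |
|---|---|---|
| 10% positive, 50/50 | 135 | 270 |
| 5% positive, 50/50 | 142.5 | 285 |
| 5% positive, smaller stratum of 40/60 | 114 | 228 |
| HIV-positive at 5% to 10% | 15 to 30 | 30 to 60 |
| Same, if only the 70% who take the healer test can be found positive | 10.5 to 21 | 21 to 42 |

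The 5% in the text does not produce 135 under either total. The expected 10 to 30 HIV-positive participants matches the span for 300 (10.5 to 30), not that for 600 (21 to 60).

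**Step 3: reproduce the tables at their own n.** A two-sided Wald test on log RR with robust variance (modified Poisson with one binary covariate) was simulated 40,000 times per cell. Results at 30% uptake and RR 2.0:

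| Component share | Table 1 | Simulated, n=135 | Simulated, n=270 | Table 2 | Simulated, n=115 | Simulated, n=228 |
|---|---|---|---|---|---|---|
| 50% | 0.928 | 0.939 | 0.999 | 0.902 | 0.894 | 0.997 |
| 60% | 0.924 | 0.922 | 0.998 | 0.852 | 0.871 | 0.995 |
| 70% | 0.850 | 0.867 | 0.994 | 0.796 | 0.795 | 0.984 |

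Over all 60 cells of each table, simulated minus tabulated power averages +0.004 at n=135 and +0.003 at n=115. In each table 48 of 60 cells agree within 2 points, and the largest gaps are 3.7 and 4.4 points. The protocol used 500 runs per cell, so its Monte Carlo standard error is up to √(0.5 × 0.5 / 500) = 0.022, and gaps of that size are expected. The tables are therefore correct for 135 and 115.

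**Step 4: compare with the strata 600 would give.** The average gap rises to +0.128 at n=270 (17 of 60 cells within 2 points), +0.133 at n=285 (16 of 60) and +0.155 at n=228 (13 of 60). Most remaining matches are cells already near 1. At 20% uptake and RR 2.25, n=270 gives 0.977 to 0.994 for shares of 70% down to 50%. At 30% uptake and n=270, 80% to 90% power is reached at an RR of about 1.56 to 1.74, depending on the share.

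**Step 5: text against its own tables.** At the 70% share expected for healer testing, Table 1 gives 0.850 where the text says about 90%, and 0.762 where it says more than 80%. Table 2 gives 0.796 where the text says at least 80%.

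**The case against.** The strongest reply is that the tables themselves contain no error. Each row is labelled with its own n, and if 600 are enrolled the tabulated powers are lower bounds, so the mistake is conservative. The study is a non-randomised pilot that already concedes limited power in small subgroups, and no confirmatory test or stopping rule rests on these tables. The direction is right, and it means the mismatch does not leave a 600-person study underpowered. It does not settle which total applies, and an enrolment target that is uncertain by a factor of two is itself a defect.

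The HIV-positive count is the weakest strand: 30 is also 5% of 600, and the ART analysis is called underpowered in any case. The range as a whole still fits 300 better, with or without the 70% test-uptake discount, and the finding stands without it.

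A fair caution is that the powers for 600 assume independent participants, complete outcomes and unadjusted comparisons. Participants are recruited through individual healers and choose their own components, and the documents give no figure for clustering or loss. Purely as an illustration, a 1.5- to 2-fold loss of effective n would put power for RR 2.0 at 0.98 to 0.87 (n=270) and 0.96 to 0.79 (n=228) for shares of 50% to 70%. The recomputed figures are therefore upper bounds, made on the same assumptions as the protocol's own tables.

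**Conclusion.** The concern holds. The text and its tables describe studies that differ two-fold in size, and nothing in the document explains the difference.

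- **If 600 is right:** power for RR 2.0 at 30% uptake is 0.98 to above 0.99, not about 90%, and the expected HIV-positive count is 30 to 60 (21 to 42 at 70% test uptake), not 10 to 30.
- **If about 300 is right:** the tables stand, the enrolment figure is double what they support, and the three power sentences still fail at the 70% component share.

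The back-calculation uses only the document's numbers. The power figures rest on two-sided alpha of 0.05 and the independence and completeness conditions above. The document does not show which total is current, so the sponsor must say.

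**What to change.** 1. State one total sample size, and one HIV-positive percentage used in both the text and the footnotes.
2. Rerun the existing simulation at the matching strata: 270 or 285 (50/50) and 228 (40/60) for 600; 135 or about 143, and 114, for 300. State alpha.
3. Restate the three power sentences so that they hold at the 70% component share, or name the shares to which they apply.
4. Restate the expected HIV-positive count: 30 to 60 for 600 (21 to 42 at 70% test uptake), or 15 to 30 for 300 (10.5 to 21), and say which basis is used.
5. If the drop from 600 to about 300 was meant as an allowance for attrition or clustering, say so and give the figure.

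The cost is one rerun of an existing simulation and edits to two tables and the surrounding sample-size text. The design does not change.

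### For healer testing (70% uptake), Table 1 shows less power than the text claims, and the tables' strata fit about 300 participants, not the stated 600

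*Combined protocol and SAP*

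**What the plan says.** All the text below is in section 4, Calculation of Sample Size & Sampling Strategy, with Tables 1 and 2.

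- Planned uptake of the three components: "70% will complete the healer-initiated HIV test, 60% will participate in additional counseling sessions, and 50% will attend an open house". Healer testing is therefore the 70% row of each table.
- Expected endpoint rate: "we anticipate the primary endpoint of uptake of HIV testing at the health facility will be low, approximately 30" percent. The 30% rows are the planning case.
- Basis of the power statements: "Given our sample size of 600 study participants, with 5% testing HIV+, and for a modifying variable distributed 50%/50" percent.
- First power statement: "we have ~90% power to detect stratum-specific RRs of 2.0 for each intervention component (Table 1").
- Second: "We still retain >80% power to detect RRs of 2.25 even if uptake of HIV testing in control group is as low as 20" percent.
- Third, for a 40/60 modifier: "we retain ≥80% power to detect stratum-specific RRs of 2.0 (Table 2").

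Table 1 is computed for strata of 135. Its footnote derives this from roughly 10% HIV-positive exclusions followed by an equal split. Table 2 is computed for strata of 115, which its footnote derives from roughly 5% exclusions and a 40% stratum. Each cell rests on 500 simulations.

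**The concern.** The text cites the tables as the source of its power figures, so the two should agree. For healer testing, the component the pilot is built around, two of the three figures do not. A reader who relies on the text would take a null healer-testing result within a stratum as backed by 80 to 90% power, when the cited table shows 76 to 85%.

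The mismatch also exposes a second one. The stratum sizes in the tables cannot be obtained from 600 participants, so neither the text nor the tables can be taken as the study's power until the total is settled.

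**Working it through.** **1. Text against the printed cells**

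| Statement | 50% row | 60% row | 70% row (healer test) |
|---|---|---|---|
| About 90%: RR 2.0, baseline 30%, Table 1 | 0.928 | 0.924 | 0.850 |
| Over 80%: RR 2.25, baseline 20%, Table 1 | 0.868 | 0.824 | 0.762 |
| At least 80%: RR 2.0, baseline 30%, Table 2 | 0.902 | 0.852 | 0.796 |

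The 50% and 60% rows support the text throughout. The 70% row does not. For the second statement it reads "0.346 0.576 0.762" across RR 1.75, 2.0 and 2.25.

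**2. Is the gap simulation noise?** With 500 runs, SE = √(p(1−p)/500) and the 95% interval is p ± 1.96 SE.

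- 0.850: SE 0.016, interval 0.819 to 0.881. This excludes 0.90.
- 0.762: SE 0.019, interval 0.725 to 0.799. This lies just below 0.80.
- 0.796: SE 0.018, interval 0.761 to 0.831. This includes 0.80, so the third statement is not contradicted.

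**3. Are the printed cells right for their stratum size?** Section 7 plans modified Poisson regression. With one binary covariate this is a Wald test on the log RR with robust variance. Alpha is not stated, so two-sided 5% is assumed from the 95% intervals. Simulated power for the 70% component:

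- n = 135, RR 2.0, baseline 30%: 0.863 to 0.866 (printed 0.850).
- n = 135, RR 2.25, baseline 20%: 0.765 to 0.767 (printed 0.762).
- n = 115, RR 2.0, baseline 30%: 0.796 to 0.801 (printed 0.796).

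The cells reproduce. A pooled two-proportion formula gives 0.907, 0.812 and 0.855, which would meet the text. It is not the planned model, and it is not what the tables print.

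**4. Which total do the strata imply?** Stratum size = total × (1 − HIV-positive share) × stratum share.

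- Table 1 footnote (10%, 50%): 600 × 0.90 × 0.50 = 270; 300 × 0.90 × 0.50 = 135 (printed 135).
- Table 2 footnote (5%, 40%): 600 × 0.95 × 0.40 = 228; 300 × 0.95 × 0.40 = 114 (printed 115).
- Text basis for Table 1 (5%, 50%): 600 × 0.95 × 0.50 = 285.

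Both tables fit a total of about 300. The same section expects 10 to 30 participants to test positive. At its 5 to 10%, a total of 600 gives 600 × 0.05 = 30 to 600 × 0.10 = 60, and a total of 300 gives 15 to 30. The documents do not settle which total is meant.

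**5. Power for the 70% component with strata derived from 600** (same simulation; pooled formula in brackets)

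| Stratum n | RR 2.0, baseline 30% | RR 2.25, baseline 20% |
|---|---|---|
| 285 | 0.996 (0.998) | 0.984 (0.989) |
| 270 | 0.995 (0.997) | 0.979 (0.985) |
| 228 | 0.984 (0.990) | 0.950 (0.965) |

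**6. Effect of the 5% versus 10% mismatch if the total is about 300.** 300 × 0.95 × 0.50 = 142.5. At n = 142 the 70% component has 0.887 at RR 2.0 (baseline 30%) and 0.790 at RR 2.25 (baseline 20%). The first could then pass as about 90%. The second would still miss the text's figure, narrowly.

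**The case against.** The strongest reply is that the study states 600 participants. At that size every power statement is met or exceeded for healer testing, so regenerating the tables would remove the shortfall. This stands as a limit on the point. A reader might infer from the 70% rows that healer testing is underpowered, and the documents support that only if the real total is about 300. Writing 85% and 76% into a 600-participant protocol would be wrong. The reply does not remove the disagreement between the text and the tables it cites, and correcting the total alone would leave one figure standing for three components whose power differs.

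The wording can also be defended. Only the first statement explicitly covers every component, and its three cells average (0.928 + 0.924 + 0.850)/3 = 0.90. That makes it a loose summary, but a claim about each component is not met by an average. The second statement carries no such qualifier, though it follows directly from the first and does not exempt healer testing.

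The consequences are limited. Section 9 calls this a non-randomised pilot and warns of low power in small subgroups, and the 70% rows are printed for anyone to read. No analysis or decision rule depends on the figures.

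A reader might also infer that the tables should extend to 80% or 88% uptake, because the Introduction reports that "index, self, mobile, and door-to-door testing achieved the highest uptake (88%, 87%, 87% and 80%, respectively"). Those figures concern other ways of testing. The protocol plans 70% for healers, so such rows are an optional sensitivity check and their absence is not an error.

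**Conclusion.** The text and Table 1 disagree for healer testing in two places: 0.850 against about 90%, and 0.762 against more than 80%. The third comparison, 0.796 against at least 80%, is within simulation error and is not a contradiction.

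The larger inconsistency lies underneath. Strata of 135 and 115 fit about 300 participants rather than 600, and Table 1 uses about 10% HIV-positive where the text says 5%. Depending on which total is right, healer-testing power at RR 2.0 with 30% baseline uptake is about 0.85 or at least 0.98. At RR 2.25 with 20% it is about 0.76 or 0.95 to 0.98. The documents do not say which applies, so they do not show that healer testing lacks power.

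These figures assume a two-sided 5% test and the planned model with one binary covariate. They make no allowance for loss to follow-up, confounding or clustering by healer.

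**What to change.** 1. Confirm the total sample size and the HIV-positive share, and use the same stratum sizes in the text and both tables.
2. Replace the single figure with power stated separately for healer testing (70%), counseling (60%) and Open House (50%).
3. If the 135 and 115 strata stand, correct the stated total. For healer testing give about 85% (RR 2.0, 30% uptake) and about 76% (RR 2.25, 20% uptake), and keep the about-90% and over-80% wording for the other two components.
4. If 600 stands, rerun both tables for the matching strata (285 or 270, and 228) and quote the resulting figures.
5. State alpha. Rows for 80% and 88% uptake are optional.

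The cost is one rerun of the existing simulation and a few sentences. Neither the design nor the analysis changes.
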